Figure 3-2. Cohort 6 Visit Schema.....38

PROTOCOL SYNOPSIS

Gilead Sciences, Inc.
[name]
[name]

Study Title: A Phase 1b, Randomized, Blinded, Placebo-Controlled Dose-Escalation Study of the Safety and Biological Activity of GS-9620 in HIV-1 Infected, Virologically Suppressed Adults

IND Number: 122452
EudraCT Number: Not Applicable
Clinical Trials.gov Identifier: NCT02858401

Study Centers Planned: Multiple centers in North America

Objectives: The primary objectives are:

- To evaluate the safety and tolerability of escalating, multiple doses of GS-9620 in HIV-1 infected virologically suppressed adults on antiretroviral therapy (ART)
- To evaluate the virologic effect of GS-9620 as measured by changes in plasma HIV-1 RNA

The secondary objectives are:

- To evaluate the plasma pharmacokinetics (PK) of GS-9620
- To evaluate the pharmacodynamics (PD) of GS-9620 as measured by changes in interferon-stimulated genes (ISGs) and serum cytokines in whole blood compared to placebo
- To evaluate effects of GS-9620 on whole blood immune cell activation (T cell, B cell, NK cell)

The exploratory objectives are:

█ [REDACTED]

█ [REDACTED]

[REDACTED]

Study Design:

This is a randomized, double-blinded, multi-cohort dose-escalation study with dose cohorts: Cohort 1 (1 mg Dose), Cohort 2 (2 mg Dose), Cohort 3 (4 mg Dose), Cohort 4 (6 mg Dose), Cohort 5 (8 mg Dose), Cohort 6 (three administrations of 10 mg Dose, followed by seven administrations of 12 mg Dose; SEC review of the 10mg safety data will be required prior to dose escalating to 12mg), and optional Cohort 7 CCI

[REDACTED]

Two additional optional adaptive cohorts, Cohort 8 CCI and Cohort 9 CCI

[REDACTED]

[REDACTED]

For each cohort, eight subjects will be randomized in a 6:2 ratio to receive GS-9620 or placebo.

Subjects will receive a total of either 6 doses in Cohorts 1 to 3, 10 doses in Cohorts 4 to 6, CCI of their assigned study treatment administered once every other week. For all subjects in Cohort 6, Dose 4 (Day 43) will

occur after SEC review has been completed. If dose escalation is approved by the SEC, subjects in Cohort 6 will receive 12 mg of GS-9620 or placebo from Doses 4 to 10; if dose escalation is not approved by the SEC, subjects will continue receiving 10 mg of GS-9620 or placebo from Doses 4 to 10.

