The Investigator will verify the subject's continued eligibility for dosing at post-Baseline dosing visits, including the absence of dose-limiting toxicities (DLTs) and (for females of childbearing potential) a negative urine pregnancy test, prior to dosing. All doses will be directly administered by blinded site staff. Subjects will fast for 2 hours after dosing for all cohorts. After Dose 1, subjects will remain on site for 12 hours after dosing for safety assessment and phlebotomy.

Safety:

Solicitation of AEs and concomitant medications and symptom-directed physical examination at every visit.

Hematology, serum chemistry, and urinalysis weekly for Cohorts 1 to 3. For **Cohorts 4 to 9** these labs will be collected on dosing days, seven days post dose (starting from Dose 4), at end of study, and ESDD. For **Cohorts 6** CCI these labs will also be collected on Day 2 and two days post dose (starting from Dose 5).

CCI

Urine pregnancy test (for females of childbearing potential) prior to each dose.

Vital signs (blood pressure, pulse, respiration rate and temperature) at all dosing visits.

Subjects will be instructed to contact the site immediately if any flu-like symptoms are noted (eg, fatigue, pyrexia, chills, myalgia, joint pain or headache).

Pharmacokinetics:

Plasma GS-9620 concentrations will be collected at the following time points **for all cohorts**:

- Pre-dose (≤ 5 minutes prior to dosing), 0.5, 1, 2, 4, 6, 8, 10, and 12 hours post dose at Day 1; then one sample 48 hours post dose at Day 3
- **If the SEC approves the dose escalation to 12 mg in Cohort 6, starting from Dose 4 and onwards**, plasma GS-9620 concentrations will also be collected on Day 43 (Dose 4): Pre-dose (≤ 5 minutes prior to dosing), 0.5, 1, 2, 4, 6, 8, 10, and 12 hours post dose; then one sample 48 hours post dose at Day 45

CCI

A single trough ARV PK sample will be collected at Pre-Baseline/Day -13 (**Cohorts 1 to 3**) or at Screening, Day 29, Day 57, Day 85 and Day 99 (**Cohort 5**), or at Screening, Day 57 and Day 99 (**Cohorts 6** CCI CCI

The timing of the ARV trough collection is to be 20-24 hours following the subject's previous QD regimen dose and before next ARV dose (and, for any subject on a regimen containing a BID component, the trough collection must also occur 8-12 hours following the subject's previous dose of that BID component and before next ARV dose). These samples may be analyzed to assess interim ART adherence.

Pharmacodynamics:

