 - 6.4.2.4.2. Hematology profile: complete blood count (CBC) with differential and platelet count (**Days 59 and 129 only**)
 - 6.4.2.4.3. Plasma HIV-1 RNA (TaqMan® v2.0)
 - 6.4.2.4.4. Serum for cytokine/soluble biomarker studies
 - 6.4.2.4.5. Whole blood ISG mRNA panel
 - 6.4.2.4.6. Cell-associated HIV-1 RNA/DNA with stored PBMC
 - 6.4.2.4.7. Plasma HIV-1 RNA Single Copy Assay with stored plasma
 - 6.4.2.4.8. Whole blood for immune cell activation (T, B, NK)
 - 6.4.2.4.9. GS-9620 plasma pharmacokinetic assessment (Day 3 only)

6.4.3. Treatment Assessments on Non Dosing Days 8, 22, 36, 50, 64, 78, 92, 106, 120 and 134

All study visits are to be scheduled relative to the Baseline/Day 1 visit. Study visits on Days 8, 22, 36, 50, 64, 78, 92, 106, 120 and 134 are to be completed within \pm 1 day of the protocol specified visit date. The following procedures will be performed:

- 6.4.3.1. Review of AEs and changes in concomitant medications
- 6.4.3.2. Symptom-directed physical examination as needed
- 6.4.3.3. Urine collection for urinalysis (**Days 50, 64, 78, 92, 120 and 134 only**)

- 6.4.3.4. Blood sample collection for the following laboratory analyses:
 - 6.4.3.4.1. Chemistry profile: alkaline phosphatase, AST, ALT, total bilirubin, direct and indirect bilirubin, total protein, albumin, CPK, bicarbonate, BUN, calcium, chloride, creatinine, glucose, phosphorus, magnesium, potassium, sodium, uric acid **(Days 50, 64, 78, 92, 120 and 134 only)**
 - 6.4.3.4.2. Hematology profile: complete blood count (CBC) with differential and platelet count **(Days 50, 64, 78, 92, 120 and 134 only)**
 - 6.4.3.4.3. Plasma HIV-1 RNA (TaqMan[®] v2.0)
 - 6.4.3.4.4. CD4+ cell count **(Days 50, 64, 78, 92, 120 and 134)**
 - 6.4.3.4.4.1. CD8+ cell count, CD4/CD8 ratio and CD4 % **(Days 50, 64, 78, 92, 120 and 134 for Cohorts 5 to 9 only)**
 - 6.4.3.4.5. Serum for cytokine/soluble biomarker studies **(Days 50, 64 and 134 only)**
 - 6.4.3.4.6. Whole blood ISG mRNA panel **(Days 50, 64 and 134 only)**
- 6.4.4. Treatment Assessments on Dosing Days 15, 29, 43, 57, 71, 85, 99, 113 and 127**

Subjects are to arrive in a fasting state for the Dosing Days 15, 29, 43, 57, 71, 85, 99, 113 and 127 and to follow fasting and food/liquids consumption requirement shown in 1. Initiation of the treatment with the study drug must take place in the clinic and will be administered by blinded study staff.

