 - 6.4.4.7.8. Whole blood ISG mRNA panel **collected pre-dose (Day 43 for Cohort 6 subjects who receive 12 mg at Dose 4; Days 57 and 127 for all subjects)**
 - 6.4.4.7.9. Plasma HIV-1 RNA Single Copy Assay with stored plasma **collected pre-dose (Days 57 and 127 only)**
 - 6.4.4.7.10. Whole blood for immune cell activation (T, B, NK,) and FoxP3+Treg level **collected pre-dose (Days 57 and 127 only)**

6.4.4.7.11. Pharmacokinetic Blood Collection (**only if the SEC approves the dose escalation to 12 mg in Cohort 6, starting from Dose 4 and onwards**)

Intensive PK sampling will occur at the following time points

- Pre-dose (≤ 5 minutes prior to dosing), 0.5, 1, 2, 4, 6, 8, 10, and 12 hours post dose at Day 43;
- Then one sample on Day 45 (48 hours post dose)

Details of pharmacokinetic blood sampling procedures and sample management for all PK samples in the study will be documented in the Pharmacokinetic Sample Collection, Processing, Storage, and Shipment Manual.

6.4.4.8. The Investigator will verify the subject's continued eligibility for in-clinic dosing, including the absence of DLTs described in Section 7.6.1.

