6.4.4.9. In-Clinic Dosing

6.4.5. Treatment Assessments on Non Dosing Days 31, 45, 73, 87, 101 and 115 (For Cohorts 5 to 9 only)

All study visits are to be scheduled relative to the Baseline/Day 1 visit. Study visits on Day 31, Day 45, Day 73, Day 87, Day 101 and Day 115 Day are to be completed within ± 1 day of the protocol specified visit date. The following procedures will be performed:

- 6.4.5.1. Review of AEs and changes in concomitant medication
- 6.4.5.2. Symptom-directed physical examination as needed
- 6.4.5.3. Urine collection for urinalysis (**Days 73, 87, 101 and 115 only**)
- 6.4.5.4. Blood sample collection for the following laboratory analyses:
 - 6.4.5.4.1. Chemistry profile: alkaline phosphatase, AST, ALT, total bilirubin, direct and indirect bilirubin, total protein, albumin, CPK, bicarbonate, BUN, calcium, chloride, creatinine, glucose, phosphorus, magnesium, potassium, sodium, uric acid (**Days 73, 87, 101 and 115 only**)
 - 6.4.5.4.2. Hematology profile: complete blood count (CBC) with differential and platelet count (**Days 73, 87, 101 and 115 only**)
 - 6.4.5.4.3. Plasma HIV-1 RNA (TaqMan[®] v2.0)
 - 6.4.5.4.4. Serum for cytokine/soluble biomarker studies (**Day 45**, only if the SEC approves the dose escalation to 12 mg in Cohort 6 starting from Dose 4)
 - 6.4.5.4.5. Whole blood ISG mRNA panel (**Day 45**, only if the SEC approves the dose escalation to 12 mg in Cohort 6 starting from Dose 4)

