7.6. Toxicity Management

7.6.1. Management of Dose-Limiting Toxicities (DLTs)

Prior to the subject being administered the in-clinic dose the Investigator will verify the subjects continued eligibility for dosing, including the absence of DLTs listed below:

- ALT elevation as defined as:
 - $ALT \geq 10 \times ULN$ **OR**
 - Confirmed ALT elevation (ie. Grade shift or $2 \times$ previous value) with evidence of worsened hepatic function (e.g. total bilirubin $> 2\text{mg/dL}$ above Baseline, serum albumin $> 1\text{ g/dL}$ decrease from Baseline)
- A confirmed \geq Grade 3 AE considered drug related by the Investigator
- A confirmed, clinically significant \geq Grade 3 laboratory abnormality considered study drug-related by the investigator
- A persistent (≥ 72 hours) \geq Grade 2 flu-like symptom (pyrexia, fatigue, myalgia, arthralgia, headache, chills) considered study drug-related by the investigator
- A post-dose increase in plasma HIV-1 RNA that fails to resolve to < 50 copies/mL within 10 days in Cohorts 1 to 3
- A post-dose increase in plasma HIV-1 RNA that fails to resolve to < 200 copies/mL within 10 days in Cohorts 4 to 9

The designated Safety Evaluation Committee contact will be notified within 24 hours of the Investigator's knowledge of a subject having any of the above DLTs. Dosing must be withheld until the Safety Evaluation Committee determines the appropriate next steps, including but not limited to additional safety, pharmacokinetic and pharmacodynamic assessments. The SEC may also suspend dosing in additional subjects or cohorts.

The SEC may hold or discontinue study drug dosing for a subject if they receive GS-9620 and experience one or more DLTs. The SEC may hold or discontinue study drug dosing for a cohort if ≥ 2 out of 6 subjects receiving GS-9620 experience one or more DLTs.

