7.6.2. Management of Other Toxicities

Unless otherwise specified in Section 7.6.1, toxicities will be managed according to the guidelines below.

- All clinical and clinically significant laboratory toxicities will be managed according to uniform guidelines detailed in [Appendix 3](#).
- Grade 3 and 4 clinically significant laboratory abnormalities should be confirmed by repeat testing within 3 calendar days of receipt of results and before investigational medicinal product (IMP) discontinuation, unless such a delay is not consistent with good medical practice.
- Clinical events and clinically significant laboratory abnormalities will be graded according to the Table for GSI Grading Scale for Severity of Adverse Events and Laboratory Abnormalities ([Appendix 4](#)).
- When restarting IMP following resolution of the adverse event, the investigational medicinal product should be restarted at full dose or modified dose that is dependent upon discussion with the Gilead Sciences Medical Monitor.
- Any recurrence of the Grade 3 or 4 clinical or clinically significant laboratory adverse event following dose interruption mandates permanent discontinuation of IMP.
- Any questions regarding toxicity management should be directed to the Gilead Sciences Medical Monitor.

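### Cohort 6: if 12 mg is approved, the first 12 mg dose (Day 43) has no scheduled post-dose safety labs until Day 50, although a Day 45 blood draw is already planned; adding them there is a cheap improvement

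*Protocol*

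**What the plan says.** **Dose.** Under Study Design, the protocol synopsis states that, with SEC approval, "subjects in Cohort 6 will receive 12 mg of GS-9620 or placebo from Doses 4 to 10". Dose 4 falls on Day 43.

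**Safety labs.** Under On-Study Procedures (Safety), the synopsis sets labs for Cohorts 4 to 9 on dosing days and at seven days post dose from Dose 4. For Cohort 6 it adds that "these labs will also be collected on Day 2 and two days post dose (starting from Dose 5"). The visit sections agree:

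- Section 6.4.1 gives labs on Day 2.
- Section 6.4.2 gives labs on Days 59 and 129.
- Section 6.4.5, which covers the Day 45 visit, limits urinalysis, chemistry and hematology to "Days 73, 87, 101 and 115 only".
- Section 6.4.3 lists the seven-day labs as "Days 50, 64, 78, 92, 120 and 134 only", so Day 50 is the first.

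In SAP Appendix 2 (Cohorts 5 to 9), all three lab rows are blank at Day 45 and marked at Day 50.

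**What Day 45 does contain.** It has adverse-event review, a symptom-directed examination and plasma HIV-1 RNA. Cytokine and ISG samples are added "only if the SEC approves the dose escalation to 12 mg in Cohort 6 starting from Dose 4". Section 6.4.4.7.11 adds the PK draw: "Then one sample on Day 45 (48 hours post dose").

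**What a laboratory finding can trigger.** Section 7.6.1 makes a confirmed, clinically significant "Grade 3 laboratory abnormality considered study drug-related by the investigator" (that grade or higher) a dose-limiting toxicity (DLT). ALT at or above 10 × ULN is a separate DLT, and its wording does not ask for confirmation. Under Section 7.6.2, Grade 3 and 4 clinically significant abnormalities "should be confirmed by repeat testing within 3 calendar days of receipt of results".

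**The concern.** The protocol adds early labs to Cohort 6 beyond the general rule for Cohorts 4 to 9, and these cover every 12 mg dose except the first. That dose is the first exposure in this study to the highest planned dose. For PK, cytokines and ISGs it is sampled as a new dose level; for safety labs it is not. The unredacted text gives no reason.

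Laboratory DLTs lead to withheld doses and count toward the rule under which a cohort may be suspended when 2 of 6 active subjects have a DLT. A later first look leaves less time to confirm an abnormality before Dose 5. It could also miss a short-lived one. Section 1.4 reports that in hepatitis B and C patients, at doses up to 4 mg, ISG15 peaked within 48 hours and was back to baseline within 7 days. Day 45 therefore sits near that peak and Day 50 near its end. This is only a reason to look early: the documents do not show that safety labs follow the same course.

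**Working it through.** The plan has no figure to reproduce here, so the check rebuilds the lab calendar.

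**Inputs.** Dose k is on Day 1 + 14(k − 1). Post-dose lab days come from Sections 6.4.1, 6.4.2, 6.4.3 and 6.4.5, and dosing-day labs from 6.4.4. Dosing-day labs are taken as pre-dose because 6.4.4 lists the blood draw, then the DLT check, then dosing.

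**First scheduled labs after each Cohort 6 dose, if 12 mg is approved**

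| Dose | Day | Level | First labs after dose | Offset |
|---|---|---|---|---|
| 1 | 1 | 10 mg | Day 2 | +1 |
| 2 | 15 | 10 mg | Day 29 | +14 |
| 3 | 29 | 10 mg | Day 43 | +14 |
| 4 | 43 | 12 mg (first) | Day 50 | +7 |
| 5 to 10 | 57, 71, 85, 99, 113, 127 | 12 mg | Days 59, 73, 87, 101, 115, 129 | +2 each |

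So 6 of the 7 doses at 12 mg have +2-day labs. Day 50 has a ±1-day window: 49 − 43 = 6 and 51 − 43 = 8, a gap of +6 to +8 days.

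**How much earlier Day 45 would be.** 50 − 45 = 5 days. With ±1 day on both visits the range is 49 − 46 = 3 to 51 − 44 = 7 days.

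**Margin before Dose 5 (Day 57) for an abnormality that needs confirmation.** Assume results arrive 0 to 3 days after the draw (the documents give no turnaround) and the retest takes the full 3 days allowed by Section 7.6.2. The retest's own turnaround is not counted. Retest day = draw day + delay + 3; margin = 57 − retest day.

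| First draw | Earliest retest | Latest retest | Margin |
|---|---|---|---|
| Day 50 ±1 | 49 + 0 + 3 = Day 52 | 51 + 3 + 3 = Day 57 | 5 to 0 days |
| Day 45 ±1 | 44 + 0 + 3 = Day 47 | 46 + 3 + 3 = Day 52 | 10 to 5 days |

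**Abnormalities that need no confirmation.** A single ALT at or above 10 × ULN is a DLT as Section 7.6.1 is worded. A value above that line on Day 45 and below it by Day 50 would be recorded as a DLT only if chemistry were drawn on Day 45. By contrast, a brief change that resolves before retest would not meet the confirmed Grade 3 criterion on either schedule.

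**Blood volume.** The limit in the synopsis is 473 mL per 56 days. Already in play:

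- Two intensive PK profiles between Day 1 and Day 45, each 9 samples to 12 h plus one at 48 h: 2 × 10 = 20 samples.
- The conditional cytokine and ISG draws on Days 43, 45 and 50.
- Possibly the Pre-Baseline draws. That visit has a ±3-day window, and Day −10 is 45 + 10 = 55 days before Day 45.

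The documents give no volumes. If one set takes 5 to 15 mL (assumption), it uses 5/473 = 1.1% to 15/473 = 3.2% of the limit.

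**The case against.** A reader might infer that subjects go a week at the top dose without safety monitoring. The documents do not support that. The same subjects have had three 10 mg doses and an SEC review. The step from 10 to 12 mg is 2/10 = 20%, the smallest relative step in the study. Day 45 has adverse-event review and an examination, subjects are told to report flu-like symptoms at once, and unscheduled tests remain possible. Day 50 labs, Day 57 labs and a DLT check all precede the second 12 mg dose. In the single-dose study in healthy subjects (Section 1.2.3.1), nobody stopped for laboratory abnormalities, and the Grade 3 events described at 12 mg were pyrexia.

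Nor can a reader infer that lower doses were watched more closely overall. At 1, 2 and 4 mg, hematology was drawn at +2 days but chemistry and urinalysis first at +7. At 6 and 8 mg, the synopsis schedules no labs after Dose 1 until Day 15 (+14). Within Cohort 6, Doses 2 and 3 also wait 14 days, but they repeat a dose already given.

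The sampling of Dose 4 as a new level is partial: cell-associated HIV RNA/DNA, single-copy assay and immune-cell activation are not taken around it. A volume-driven choice cannot be ruled out, though the documents do not state one.

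These points limit the size of the concern. They do not explain why the first 12 mg dose is the one left out. Two of the safeguards are also weaker than they look: Day 57 labs are drawn on the day of Dose 5, so with turnaround unstated they may not inform it, and the Day 50 route can leave no margin if the draw, result and retest all run late.

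**Conclusion.** The gap is real but modest, and closing it is a worthwhile low-cost improvement. If 12 mg is approved, the first 12 mg dose is the only one of seven without +2-day labs, and its first look comes at +6 to +8 days. Drawing on Day 45 brings that look forward by 5 days (3 to 7 with windows) and raises the margin before Dose 5 from 0–5 to 5–10 days, on the turnaround assumption above. It would also catch an ALT peak at the unconfirmed DLT threshold that had subsided by Day 50. Whether such a peak occurs, or could fall that quickly, is not known from the documents.

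This is not a demonstrated safety defect, and no dosing decision is shown to be wrong. The point concerns scheduled labs only, at one visit in 8 subjects (6 on active drug), and only if the SEC approves 12 mg.

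**What to change.** For Cohort 6, when 12 mg is given at Dose 4, add Day 45 to Sections 6.4.5.3 (urinalysis), 6.4.5.4.1 (chemistry) and 6.4.5.4.2 (hematology), and to the Cohorts 5 to 9 procedures table. Amend the synopsis so that the two-day post-dose labs start from Dose 4 if 12 mg is given at Dose 4, and otherwise from Dose 5. Update the SAP copy of the table to match.

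The cost is one extra lab set per Cohort 6 subject (8 in all) at a visit where blood is already drawn. Before adopting it, check the 473 mL per 56 days limit against actual tube volumes, counting both PK profiles, the Day 43, 45 and 50 cytokine and ISG draws, and any Pre-Baseline draws inside the 56-day window. If the limit is tight, take only a CBC with ALT, AST and bilirubin; urinalysis needs no blood.

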1. INTRODUCTION

1.1. Background

Human immunodeficiency virus type-1 (HIV-1) infection is a life-threatening and serious disease that is of major public health interest around the world. There are approximately 2.4 million people in North America and Western and Central Europe living with HIV-1 and 36 million people worldwide {[Joint United Nations Programme on HIV/AIDS \(UNAIDS\) 2016](#)}. Untreated infection leads to deterioration in immune function and death. The availability of antiretroviral therapy (ART) has been associated with a dramatic decrease in acquired immune deficiency syndrome (AIDS)-related morbidity and mortality {[Mocroft 1998](#), [Palella 1998](#), [Sterne 2005](#)}.

While ART effectively suppresses HIV replication, HIV infection remains incurable. Persistent viral reservoirs fuel rebound viremia when treatment ceases. Despite the availability of chronic treatment, morbidity and mortality due to HIV infection remain high due to the latent HIV reservoir, which may contribute to ongoing inflammation-driven disease. Current therapy is associated with challenges with tolerability, long-term adherence and safety, drug-drug interactions, and expense. Persistent HIV infection may also be associated with psychosocial stigma. Thus, the discovery and development of therapeutic interventions that can eradicate or control HIV reservoirs, leading to long-term ART-free remission or HIV cure, is a major priority.

Following entry into a target cell, HIV-1 stably integrates into the host genome, thus establishing the basis for latent infection and the main barrier to HIV cure. Neither the host immune system nor ART can eliminate transcriptionally inactive virus. Therefore, adjunctive therapies that efficiently reactivate (“kick”) virus out of this latent reservoir to enable its destruction (“kill”) may be required for viral eradication. This “kick and kill” strategy to cure or induce long-term HIV remission has been tested in clinical trials of latency reversal agents (LRA) such as histone deacetylase inhibitors (HDACi). While short-term treatment with HDACi such as romidepsin appears to be safe and may activate viral transcription in individuals virologically suppressed on ART, the size of the latent viral reservoir as measured by total peripheral blood mononuclear cell (PBMC)-associated HIV-1 DNA or quantitative viral outgrowth assay (QVOA) appears to be unchanged {[Sogaard 2015](#)}. However, a TLR9 agonist has been dosed in HIV-1 positive participants on ART in a single-arm open-label study demonstrating increases in plasma IFN- α levels, transcriptional (messenger ribonucleic acid [mRNA] induction of interferon stimulated genes (ISGs), activation of pDCs, activation of cytotoxic natural killer (NK) and CD8+ T cells with transient increases in plasma HIV-1 RNA in a subset of individuals {[Vibholm 2017](#)}. It is postulated that a combination of therapies exerting viral latency reversing activity and engagement of the host immune system will be necessary to have a demonstrable effect on reducing the HIV-1 reservoir. To date there is no fully validated biomarker for the latent HIV-1 reservoir. Therefore, measurement of the time to viral rebound and/or new viral load set-points following analytical treatment interruption (ATI) is the most accurate endpoint to evaluate the efficacy of “kick and kill” interventions. The AIDS Clinical Trials Group (ACTG) has reported that ATI can be conducted safely in patients {[Bar 2016](#), [Li 2016](#)} and that certain measures of the HIV reservoir may be correlated with time to viral rebound {[Li 2016](#)}.

GS-9620 is an orally-administered toll-like receptor (TLR) 7 agonist currently in clinical development for the treatment of HIV. In vitro, GS-9620 appears to mediate both HIV-1 “kick” and “kill” activity. In a rhesus macaque model of chronic SIV infection, treatment with GS-9620 or its close analog GS-436986 has also demonstrated the ability to both “kick” and “kill”: treatment resulted in transient detection of plasma viremia within 24-72 hours of dosing, decreases in ex vivo SIV production from T-cell receptor stimulated PBMC cultures or immune cell isolates of peripheral lymph nodes comparing pre-treatment to post-dosing samples and a $\sim 0.5 \log_{10}$ lower viral load set-point after discontinuation of ART {Lim 2018}. Most importantly, in a subset of animals, there was a lack of detectable plasma virus (< 50 SIV RNA copies/mL) for > 2 years after discontinuation of ART. During the off ART phase, two animals from one of the studies had no viral rebound after administration of antibodies depleting NK and CD8+ lymphocytes or transfer of viral infection after infusion of mononuclear immune cells from lymph node and peripheral blood into naïve animals; implying a substantial reduction in viral reservoir. The administration of multiple doses of GS-9620 has been shown to be safe in clinical studies of healthy subjects (single doses up to 12 mg), and hepatitis B virus (HBV)-infected subjects (multiple doses up to 4 mg). This study will therefore investigate the safety and efficacy of GS-9620 in HIV-infected individuals who are virologically suppressed on ART.

